3.1.6. Actual Treatment

In the event that a subject is dispensed incorrect treatment the following rules will be used to decide actual treatment during the period that the incorrect treatment was dispensed and returned:

Mean Dose	Actual Treatment
≤ 140 mg	80mg
> 140 mg	200mg

Mean dose is calculated over a period as the summation of each tablet taken (where placebo is considered 0mg) and divided by total number of days on treatment in the period.

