1.2.2. Definition of Study Drugs

Study drug comprises the following (placebo and 2 doses of TD-1473):

- TD-1473 80 mg once daily: Taken orally for up to 60 (including ATE) weeks in the morning before eating. Subject must refrain from eating or drinking anything other than water and non-study medications for at least 30 minutes after dosing. Subjects from placebo arm will take from start of ATE Day 1 to ATE week 48.
- TD-1473 200 mg once daily: Taken orally for up to 60 (including ATE) weeks in the morning before eating. Subject must refrain from eating or drinking anything other than water and non-study medications for at least 30 minutes after dosing.

Placebo once daily: Taken orally for up to 12 weeks in the morning before eating. Subject must refrain from eating or drinking anything other than water and non-study medications for at least 30 minutes after dosing.

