1.3. Treatment Assignment and Blinding

Central randomization for treatment allocation will be implemented. A computer-generated randomization schedule will be prepared for this study under the supervision of the sponsor.

The randomization will be stratified by history of biologic treatment failure (Yes, No) crossed with baseline CDAI category (≤ 300 , > 300). A sequence of randomly permuted blocks will be used to centrally assign subjects in each stratum to TD-1473 at 80 mg, TD-1473 at 200 mg, or placebo in a 3:3:2 ratio. Enrollment targets are shown in Table 3:

Table 3: Randomization

Stratum\Treatment Group	All Treatment Groups	Placebo once daily	TD-1473 80 mg once daily	TD-1473 200 mg once daily
All Strata	160	40	60	60

Randomization caps will be placed on both prior biologics failure subgroups (no to biologic failure (up to 60%) and yes to biologic failure (up to 60%)) to ensure that neither subgroup is overrepresented. There will also be a cap at 10% for enrollment of subjects with an SES-CD score at screening in the range of 3 to 5.

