2. ANALYSIS SETS

Table 5: Analysis Sets

Analysis Set	Definition	Treatment Assignment
Screen Failures*	Subjects who give informed written consent but are not randomized are considered screen failures. Screen failure subjects and the main reason for screen fail will be captured in the EDC.	N/A
Randomized*	The randomized analysis set will include all subjects who were randomized into the study.	Randomized treatment
Safety*	The Safety analysis set will include all subjects who received at least one dose of study drug (or placebo). The Safety analysis set is the primary analysis set for safety analyses.	Actual Treatment received (see Section 3.1.6)
ITT*	The Intent-to-Treat (ITT) analysis set comprises all randomized subjects who receive at least one dose of study drug.	Randomized treatment
Modified ITT*	The modified Intent-to-Treat (mITT) analysis set comprises all randomized subjects who receive at least one dose of study drug and have at least one postbaseline CDAI score. Only include subjects randomized prior to the 23Aug2021. The mITT set is the primary analysis set for efficacy summaries and analyses.	Randomized treatment
PP*	The Per-Protocol (PP) analysis set comprises all subjects in the mITT analysis set who complete their Week 12 visit and have no major analysis protocol deviations	Randomized treatment
Active Draining Fistulae*	The active draining fistulae analysis set comprises all subjects in the mITT analysis set with at least one draining fistula at baseline.	Randomized treatment

* Due to confirmed data integrity violations the data for site 36016 (deviation report GCP-XX) and site 38915 (deviation report GCP-11) will be excluded from all analysis sets.

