3.7. Safety Analyses

The analysis of safety and tolerability data includes an overall summary of tolerability, adverse event preferred terms by body/organ system, drug exposure (duration of treatment), dosing information/compliance clinical laboratory results, vital signs and ECGs. Tables summarizing the adverse events reported by subjects who died, experienced non-fatal serious adverse events (SAE), or prematurely discontinued the study due to adverse event (AEs) will be prepared.

In general, inferential statistical tests are not performed for adverse event incidence rates.

For all safety analyses, the safety analysis population will be used.

For summaries on exposure, compliance and adverse events for the study overall (Induction and ATE),

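### The SAP's actual-treatment rule has no placebo outcome, so a mis-dispensed period of placebo only is labelled TD-1473 80 mg

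*SAP*

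**What the plan says.** SAP 3.1.6 opens with its trigger: "In the event that a subject is dispensed incorrect treatment the following rules will be used to decide actual treatment". The classification is made "during the period that the incorrect treatment was dispensed and returned". Mean dose is the sum of the milligrams in the tablets taken, "where placebo is considered 0mg", "divided by total number of days on treatment in the period". The table that follows has two rows: a mean of 140 mg or less gives 80 mg, and a mean above 140 mg gives 200 mg. No redaction is visible in this section.

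The rule feeds the safety tables. SAP Table 5 gives the treatment assignment for the Safety set as "Actual Treatment received (see Section 3.1.6"), and SAP 3.7 says: "For all safety analyses, the safety analysis population will be used".

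Placebo is one of the treatments being classified. SAP 1.2.2 states "Study drug comprises the following (placebo and 2 doses of TD-1473"), and SAP 1.3 assigns subjects to "TD-1473 at 80 mg, TD-1473 at 200 mg, or placebo in a 3:3:2 ratio", with planned arms of 60, 60 and 40. Protocol 8.8 has Induction safety data presented according to what each subject actually received in that phase.

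**The concern.** The rule exists to put subjects in the column that matches what they took, but placebo is not among its possible results. The 80 mg row runs down to and includes 0 mg, so a subject who took nothing but placebo in the affected period is labelled as having taken active drug. That is the reverse of what classification by treatment received is meant to do.

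What is at stake is the make-up of the 80 mg and placebo columns in the safety summaries. Safety and tolerability is one of the two primary objectives, so the Safety set should be assembled by a rule that can be run as written. If the programmer has to override the rule for a 0 mg case, the decision is no longer pre-specified and may be taken after treatment codes are known.

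**Working it through.** **Inputs.**
- Cut-off 140 mg, placebo tablets valued at 0 mg, and the mean-dose formula: SAP 3.1.6.
- Doses 80 mg and 200 mg, plus placebo: SAP 1.2.2.
- Planned arms 60 / 60 / 40: SAP Table 3.
- Week 12 at nominal Day 84: SAP visit-window table (3.1.3).
- Induction dispensings at Day 1, Week 4 and Week 8: Protocol Table 1.

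**The plan's own figure.** The 140 mg cut-off is the midpoint of the two active doses: (80 + 200) / 2 = 140 mg. The SAP does not give this derivation, so it is an inference. It fits a rule built to separate 80 mg from 200 mg.

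**The rule applied literally.** Mean dose = total mg taken / days on treatment in the period. The table uses an 84-day period.

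| Intake over 84 days | Mean dose | SAP result | With 0 mg = Placebo row |
|---|---|---|---|
| Placebo only | 0 / 84 = 0 mg | 80 mg | Placebo |
| 7 days of 80 mg, rest placebo | 560 / 84 = 6.7 mg | 80 mg | 80 mg |
| 28 days of 80 mg, rest placebo | 2240 / 84 = 26.7 mg | 80 mg | 80 mg |
| 28 days of 200 mg, rest placebo | 5600 / 84 = 66.7 mg | 80 mg | 80 mg |
| 56 days of 200 mg, rest placebo | 11200 / 84 = 133.3 mg | 80 mg | 80 mg |
| 80 mg throughout | 80 mg | 80 mg | 80 mg |
| 200 mg throughout | 200 mg | 200 mg | 200 mg |

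No mean dose returns placebo. The added row changes only the first line. The result for placebo only does not depend on the length of the period: over a single 28-day interval it is 0 / 28 = 0 mg, again labelled 80 mg.

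**From period to subject.** The rule classifies the affected dispensing period. A subject who completes Induction has no drug exposure only if all three dispensings were wrongly placebo. A subject who stops early has none only if every dispensing received was wrongly placebo.

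**Size per subject, at planned arm sizes.**
- Randomized to 80 mg, took only placebo: the rule gives columns of 60 (80 mg), 60 (200 mg) and 40 (placebo); by treatment received they would be 59, 60 and 41. The rule fails to move the subject out of the 80 mg column. Share of that column: 1/60 = 1.7%.
- Randomized to 200 mg, took only placebo: the rule gives 61, 59 and 40; by treatment received they would be 60, 59 and 41. Share of the 80 mg column: 1/61 = 1.6%.
- In both cases the placebo column is short by one against a planned 40: 1/40 = 2.5%.

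These are shares per hypothetical subject, not an estimated effect. Actual columns will differ from plan, because SAP Table 5 excludes two sites from every analysis set and not every randomized subject need be dosed.

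**The case against.** The best defence is that the two rows were written for mix-ups between the active doses. They are sufficient for the Active Treatment Extension, where everyone is assigned 80 mg or 200 mg. Treating any active exposure as active is also a defensible choice in a safety analysis. Both points have force for non-zero means. Neither covers a mean of exactly 0 mg, and SAP 3.1.6 is not limited to the extension: its trigger is general, and Table 5 applies it to the whole Safety set.

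A second defence is that Protocol 8.8 and the wording of Table 5 already state the principle, so a placebo-only subject would be placed correctly in practice. The principle is there, but Table 5 points to SAP 3.1.6 for how to apply it, and the rule there gives the opposite answer.

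Several points on the other side stand and limit the finding:
- The rule covers only the period of the wrong dispensing. The SAP does not say how a period-level label becomes one column for a subject in the Induction tables.
- Dispensing runs through a central system, and repeated placebo errors for one subject would be unusual.
- Accountability, compliance and protocol deviation listings would show such a case.
- SAP 3.7 generally plans no inferential tests on adverse event incidence.

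A reader might infer that valuing placebo at 0 mg shows the authors foresaw placebo-only intake. The documents do not support that. Subjects take two tablets a day and the tablet descriptions in Protocol 5.1 are redacted, so the clause fits placebo tablets within an active regimen, or mixed periods, equally well. The finding does not depend on it.

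**Conclusion.** The gap is certain from the text; any effect on the tables is not. For a period in which a subject randomized to active drug was wrongly dispensed and took only placebo, SAP 3.1.6 gives the wrong label, in conflict with Protocol 8.8. To reach a subject's column in the Induction safety tables, the error must cover every Induction dispensing that subject received, and the period label must carry over to the subject. Then one subject is about 1.7% of the planned 80 mg arm or 2.5% of the planned placebo arm. The documents report no such subject and the number may be zero. This is a minor drafting correction.

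Three stronger readings are tempting and should be resisted:
- *Placebo subjects in general are counted as 80 mg.* They are not. The rule applies only after a dispensing error, and placebo subjects correctly given placebo are untouched.
- *The 80 mg adverse event rates are diluted.* That is hypothetical. It assumes that such a subject exists and that the drug raises event rates; for one subject it turns on whether that subject had the event.
- *The efficacy result is affected.* SAP Table 5 analyses the ITT, mITT and PP sets by randomized treatment, so it is not. Protocol 8.3 had the PP set by actual treatment; the statement here rests on the SAP's later assignment.

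**What to change.** Replace the two-row table in SAP 3.1.6 with three rows:
- mean dose 0 mg: Placebo
- above 0 mg and up to 140 mg: 80 mg
- above 140 mg: 200 mg

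This changes only the 0 mg case and leaves every non-zero classification as it stands. Extending the midpoint logic downward would put the placebo boundary at (0 + 80) / 2 = 40 mg and would reclassify means above 0 and below 40 mg, such as the 6.7 mg and 26.7 mg examples. The SAP does not choose that boundary and the correction does not need it. The sponsor may adopt it, but it is a separate decision.

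It would help to add a sentence saying how a period-level label is turned into a subject's column in the Induction summaries. The cost is one table row and one sentence. This is an analysis label only: no data collection, sample size or efficacy analysis changes.

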3.2. Study Subjects

Unless otherwise noted, the ITT analysis set is the main analysis set used in the summarization of general (Study Population) analyses.

3.2.1. Subject Disposition and Completion Status

The number of subjects screened for the study will be provided. A summary of study disposition will be provided by study treatment showing the following:

- Number of subjects randomized
- Number of subjects treated
 - Number of treated subjects who completed the study
 - Number of treated subjects who discontinued early from the study
 - Primary reasons for early study discontinuation, with frequencies
 - Number of treated subjects who completed treatment
 - Number of treated subjects who discontinued treatment early
 - Primary reasons for early treatment discontinuation, with frequencies

The following additional disposition summary will be provided:

- Number of subjects who completed the Week 12 Visit
- Number of subjects who discontinued prior to the Week 12 Visit
 - Primary reasons for discontinuation prior to the Week 12 Visit, with frequencies

A listing of subject disposition will include analysis set flags (ITT, Safety, mITT, PP [Yes/No], Active Draining Fistula), dates of first and last dose of study drug, primary reason for subject discontinuation of study treatment, study completion status, primary reason for study termination, and date of last contact.

A listing of subject eligibility (inclusion or exclusion criteria exceptions) and a listing of subjects randomized but not treated will be provided.

3.2.2. Demographic and Baseline Characteristics

Demographics

Demographic data including age, sex, race, ethnicity, weight, height, and body mass index (BMI) will be summarized overall and by treatment group. Sex, race, and ethnicity frequency distributions will be provided. Age will be further categorized as 18 to 64 vs. ≥ 65 years.

Tobacco Consumption

A summary of Tobacco Consumption taken at baseline or screening will be provided summarizing:

Parameter	Units/Response category
Tobacco Consumption Status	Never, Current, Former
Number of Tobacco Units Per Day	Converted Units
Number of Years With Tobacco Use	Years
Total Number Of Pack Years	Pack Years
Type of Tobacco Product Used	Cigarettes, Cigars, Pipe, Smokeless Tobacco

The following conversion process is used to standardize a unit of tobacco consumption:

1 unit = 1 pack (20 cigarettes) = 5 cigars = 8 pipes = 8 pinches

Number of years of tobacco use is calculated as follows where current smokers use the Day 1 Visit date as end date:

$$\frac{(\text{Tobacco use end date} - \text{Tobacco use start date} + 1)}{365.25}$$

Pack Years is calculated as number of years of tobacco use multiplied by number of tobacco units per day (converted units).

A listing will also be provided.

Crohn's Disease Clinical Characteristics

A summary of Crohn's Disease Clinical Characteristics taken at baseline or screening will be provided. A listing will also be provided.

Parameter	Units/Response category
Time since diagnosis of Crohn's disease	Years
Time Since Diagnosis categories	≤ 5years; >5 to ≤15 years; > 15 years
Extent of disease	Ileal, Colonic, Ileocolonic
Baseline CDAI score	Points
Baseline CDAI score categories	≤300 points, >300 points
Baseline Abdominal Mass	None, Questionable, Definite
Baseline average daily Abdominal Pain	None, Mild, Moderate, Severe
Baseline average daily liquid or very soft Stool Frequency	Stools
Baseline average daily total Stool Frequency	Stools
Baseline SES-CD score	Points
Upper GI Crohn's	Yes, No
██████████	██████
████████████████████	██████
██████████	
██████████████████	██████
████████████████████	██████
██████████████████	
████████████████████	██████
██████████████████	██████

Prior Crohn's Disease Therapy Characteristics

A summary of Prior Crohn's Disease Therapy Characteristics will be provided. A listing will also be provided.

Parameter	Units/Response category
Prior biologic failure	Yes, No
Prior biologic experience	Failed, Naïve, Experienced but no documented failure

Number of prior biologics failed	0, 1, 2, ≥ 3
Biologic classes failed	0, 1, 2, 3
Primary Non-responder to at least 1 Biologic	Yes, No
Secondary Non-responder to at least 1 Biologic	Yes, No
Intolerant to at least 1 Biologic	Yes, No
Oral corticosteroid use at enrollment	Yes, No
History of steroid non-response	Yes, No
History of steroid dependence	Yes, No
History of steroid dependence or non-response	Yes, No
Prior immunomodulator use	Yes, No
Prior immunomodulator non-response or intolerance	Yes, No
Prior aminosalicylate use	Yes, No
Aminosalicylate use at baseline	Yes, No
Prior aminosalicylate non-response	Yes, No
Prior Jak-inhibitor use	Yes, No

Complications of Crohn's Disease at Baseline

A summary of complications at Baseline will be provided. A listing will also be provided.

A summary of complications of Crohn's Disease at Baseline will be provided, the number and percentage of subjects with each complication collected on the Crohn's Disease History page will be presented. A listing will also be provided.

Fistula Drainage at Baseline

A summary of Fistula Drainage at Baseline will be provided. A listing of Fistula drainage over time will also be provided.

Parameter	Units/Response category
Fistula	Yes, No
Location	Small Intestine to Small Intestine, Small Intestine to Colon, Small Intestine to Bladder, Small Intestine to Skin On Abdominal Wall, Colon to Skin on Abdominal Wall, Small Intestine to Vagina, Colon to Vagina, Colon or Rectum to Skin in Pelvic Area, Small Intestine to Skin in Pelvic Area, Other
Active Drainage	Yes, No

3.2.3. Protocol Deviations

Unique subjects reporting major protocol deviations that have significant impact on primary efficacy analyses (major analysis protocol deviations) will be summarized overall and by treatment group for the ITT set.

[REDACTED]

[REDACTED]

[REDACTED]

[REDACTED]

[REDACTED]

■ [REDACTED]

[REDACTED]

[REDACTED]

■ [REDACTED]

■ [REDACTED]

A subject listing with all protocol deviations identified prior to database lock will be provided. Moreover, a listing of all major analysis protocol deviations will be provided. All subject listings will be based on the randomized analysis set.

A summary and listing of COVID-19 protocol deviations will also be presented, along with a listing of COVID-19 impacts.

3.2.4. Medical History

Medical history data will be coded using the Medical Dictionary for Regulatory Activities, version 23.0 or later. The number and percentage of subjects with medical history coded to each system organ class and preferred term will be summarized by treatment group for the safety analysis set.

3.2.5. Prior/Concomitant Medications

Prior medications include all medications taken prior to the first dose of study drug, regardless of when they were stopped. Concomitant medications include all non-study medications that the subject was taking prior to the Day 1 visit that were ongoing at the visit, in addition to all medications with a start date on or after the first dose date and no later than the last dose date + 28 days. Medications with a start date after the last dose date + 28 days will not be included in summaries but will be included in the listing of concomitant medications, with a flag.

Recorded prior and concomitant medication names from the Prior and Concomitant Medications eCRF page will be mapped according to the [REDACTED]

[REDACTED]

Prior and concomitant medication use will be tabulated separately. The number and percentage of subjects who have taken each medication will be provided by study treatment.

On-going Crohn's Disease Medications of Interest at Baseline will also be presented. Crohn's Disease Medications of Interest include aminosalicylates, corticosteroids and antibiotics for Crohn's Disease. Should a subject enter the study on prohibited biologics and immunomodulators these medications will also be presented.

On-treatment rescue medication use will be summarized. Rescue medications are defined as the following medications if used to treat CD or AE of worsening CD:

- Addition of oral corticosteroids, aminosalicylates or antibiotics
- Increase in oral corticosteroids dose up to or above baseline
- Prohibited medications

3.3. Primary Endpoint(s) Analysis

3.3.1. Definition of Primary Endpoint(s)

The primary efficacy endpoint is defined as the change from baseline in CDAI score at Week 12.

3.3.2. CDAI Score

CDAI score is calculated as sum of a Subscore x Multiplier from Appendix 5.2. The following subscores are calculated based on the most recent evaluable 7 days.

- Number of liquid or very soft stools subscore
- Average Abdominal pain subscore
- General well-being subscore

Evaluable days are defined as any non-missing diary days during the 10 days prior to the study visit. The day prior to endoscopy, day of endoscopy and the day following endoscopy will be treated as non-evaluable and treated as missing.

If fewer than 5 evaluable days data are available for any of the above subscores then the subscore is set to missing for that timepoint. If only 5 or 6 evaluable days' data are available for the above mentioned subscores then the subscore total is calculated as:

(Total score over available days/Number of available days)*7

The weight component of the CDAI will be based on ideal weight (see Section 5.3.1.4).

The CDAI score should be calculated for a visit only if ≥ 4 subscores are available at a visit, with missing subscores imputed by carrying forward the last non-missing subscore. If <4 subscores are available at a visit then the CDAI score will be set to missing.

3.3.3. Statistical Hypotheses

The primary estimate of interest, change from baseline in CDAI score at Week 12, is used to evaluate the effectiveness of therapy relative to the placebo comparator in the mITT population.

The following hypothesis testing schema will be employed to assess the primary endpoint: The null hypothesis for the treatment comparison will be that there is no difference between the mean responses at a given dose level of 1473 (active) and the mean response on the placebo treatment in change from baseline CDAI score at Week 12. The alternative hypothesis will be that there is a difference. Symbolically, this is expressed as follows:

$$H_0 : \mu_{Active} = \mu_{placebo}$$

$$H_1 : \mu_{Active} \neq \mu_{placebo}$$

In order to control for the comparison of 2 active treatment groups versus placebo for the primary endpoint, a multiplicity procedure is planned.

Only the primary endpoint is covered under multiplicity control and all other endpoints will be presented with nominal p-values.

A step-up Hochberg procedure will be used. The resulting nominal p-values for the primary endpoint will be ordered, largest to smallest.

If the largest p-value < 0.05 , then both treatment groups will be declared as statistically significant.

If the largest p-value is > 0.05 , then the smaller p-value will be compared to 0.025. If this p-value is < 0.025 , then the treatment group with the smaller p-value will be declared as statistically significant.

If no p-values meet the above conditions, the primary endpoint will be considered not statistically significant and the primary objective of the study was not met.

